3.10. Pooling of Sites and Evaluation of Site Differences

Information from the population flow chart, demographics and final disposition tables will be reported by field site to inform potential site differences. No statistical tests for differences in characteristics across field sites or between treatment groups within site will be conducted.

Except for tests of treatment-group differences in safety outcomes, which will be stratified on field site, analyses will be performed on data pooled across field sites. However, potential site-level effects will be assessed in exploratory analyses of treatment-by-site interactions for differences in proportions of subjects with TEAE and differences in the distribution of highest grade of reactogenicity observed within Day 6 of any vaccination. Interactions significant at $\alpha = 0.05$ will be described in the CSR. Site-specific tables summarizing treatment-group differences in key TEAE categories may also be produced, but formal statistical testing of treatment-by-site interactions within such categories will not be conducted. Differences in immunogenicity responses between sites may also be explored (e.g., when assessing log-normality assumptions), but no formal statistical tests of treatment by site interactions will be reported.

3.11. Multiple Comparisons

No adjustment for multiple comparisons will be made. All descriptive CIs will be at the 95% level, and all p-values assessed for statistical significance at the two-sided 0.05 level.

3.12. Interim Analyses

A formal interim immunogenicity analysis is planned for when all enrolled subjects have completed V4 (4-weeks post-primary series). The analysis will be performed by an independent statistician and shared with the Sponsor. Only treatment group-level comparisons will be provided, with no data listings which could reveal subject-level treatment assignments.

3.13. Handling missing and incomplete data

3.13.1. Premature Discontinuation and Missing Data

For any subject who withdraws prematurely from the study, all available data up to the time of discontinuation will be included in relevant analyses unless otherwise excluded during blind review. Per protocol, subjects who are discontinued from the study after vaccination (regardless of reason) will not be replaced, but a subject discontinued after randomization but prior to 1st vaccination will be replaced using a new randomization assignment for the replacing subject.

Missing data will be assumed missing at random and ignorable. Except where noted in Section 3.13.2, missing or censored data will not be estimated or imputed. Denominators for percentages will be based only on the number of subjects with non-missing values.

3.13.2. Imputed Data

All immunogenicity assays reported as being below the limit of quantification or below a specified threshold will be assigned a value of one-half the lower limit of quantification (LLOQ) or threshold value, using values of LLOQ or other information provided by the responsible laboratory. Values above an applicable upper limit of quantification (ULOQ) will be assigned the ULOQ value unless determined otherwise in blind review of data.

In the event missing event dates or times are needed to compute durations of outcomes, the following rules will be applied:

- If the month and year are known, but the date is missing, the date will be imputed as the midpoint between the earliest the event could have occurred and the latest the event could have occurred, based on reporting dates and other information in the clinical data base. If data are not available to do this, the 15th will be used for any calculations of relative time (e.g., UNMAY2018, where ‘UN’ denoted unknown, would be imputed as 15MAY2018).
- If the minutes of start or stop times are missing, time will be assumed to be on the hour for a 24 hour clock (e.g., 11:UN, is assumed to be 11:00 AM).
- Listings will report unimputed dates or times.

Otherwise, no imputation for missing values is planned.

3.14. Evaluation of Normality Assumption

The assumption of log-normality of immunogenicity data, including the impact of any imputed (below LLOQ or above ULOQ) values, will be assessed by visual inspection of quantile-to-quantile plots and tests of departures from normality. The lead statistician will use these results to determine whether the normality assumption is substantively violated; that is, if the deviation from normality is to a degree that alternative analysis methods should be employed.

If the log-normality assumption is meaningfully violated, an appropriate non-parametric or bootstrap resampling method may be considered. If bootstrap resampling is implemented, point estimates will be calculated directly from the data but CIs will use the bias-corrected and accelerated method (Efron and Tibshirani [1993]; Barker [2005]) using 10,000 bootstrap samples.

3.15. Statistical Software

Version 14.1 or higher of the SAS/STAT® software will be used for all analysis.

4. EVALUATION OF DEMOGRAPHIC AND BASELINE CHARACTERISTICS

4.1. Subject Enrolment and Disposition

Subject disposition will be summarized in a flow chart, including the numbers of subjects screened, randomized, contributing to each analysis population, reasons for early discontinuation and other exclusions from analysis populations, the percentage of subjects whose booster vaccination was delayed due to the COVID-19 pandemic, and person-time contributed to analysis, by treatment group. Disposition data (including number of vaccinations received) will also be tabulated by field site.

4.2. Protocol Deviations and Measures of Study Conduct

Protocol deviations will be reviewed during blinded data review and analysis decisions, if any, made as a consequence of these deviations documented prior to unblinding. All protocol deviations will be tabulated and listed, including individual subject unblinding, whether for safety reasons or by accident. The number of vaccination visits or home visits that were missed, and follow-up visits missed or outside of protocol window, will also be summarized.

4.3. Treatment Compliance

Treatment compliance is defined as having received all three doses of study vaccine. Randomized subjects with less than full compliance and reasons why will be listed.

4.4. Demographics and Baseline Characteristics

Demographic characteristics and socioeconomic status will be summarized for the Safety and Primary PP IMM Populations. No statistical comparisons of treatment-group differences in demographics or baseline data will be performed. Demographic data will also be reported by field site.

4.5. Medical History and Baseline Assessment

Medical history and baseline anthropometrics, vital signs, etc., will be summarized as for demographic data.

4.6. Concomitant Medications

A summary of concomitant medications taken during the study will be presented in listings and tabulated for the Safety Population. Tabulated data will use codes based on a combination of Lexicomp and the on-line Physicians' Desk Reference. Listings will include drug name, dose, route, frequency, indication, and start and end dates, as available.

5. EVALUATION OF IMMUNOGENICITY

Analysis Populations: Primary and secondary immunogenicity will be evaluated within the Primary and Secondary Per Protocol Immunogenicity Populations, as noted in Table 3.

Data Sources: Primary immunogenicity objectives will be based on serotype-specific IgG antibody concentrations measured 4 weeks after the booster vaccination series (V6). Secondary objectives will be based on the serotype-specific IgG concentrations and OPA titers at three time points (4-weeks after completion of the primary series (V4), immediately prior to booster (V5), and V6).

Endpoint Definitions:

1. **GMC [or GMT]:** The geometric mean concentration (or titer) = antilog (mean $[\log_{10} x]$), where x is the assay result
2. **Response to study vaccine:**
 - IgG concentration $\geq 0.35 \mu\text{g/mL}$
 - IgG concentration $\geq 1.00 \mu\text{g/mL}$
 - OPA titer ≥ 8

5.1. General Comments on Reporting of Immunogenicity Objectives:

1. Differences in proportions of responders to each serotype in PNEUMOSIL will be reported as the PNEUMOSIL proportion minus the reference group (Synflorix or Prevenar 13) proportion, with 95% confidence intervals calculated using the Miettinen-Nurminen (1985) likelihood score method. If the response rate is 100% in each group, then two non-response records (one for each group) will be included and given a weight of 0.000001 to facilitate computation of the 95% CI. Differences in proportions will be considered statistically significant if the 95% CI excludes 0.
2. Within-group GMCs [GMTs] and 95% CIs for each serotype in PNEUMOSIL will be computed based on the antilog (base 10) of mean log10 concentrations [titers] and the corresponding CI limits for the mean log10 values, based on a log-normality assumption.
3. Between-group GMC [GMT] ratios will be reported as the PNEUMOSIL GMC [GMT] divided by the reference vaccine GMC [GMT]. 95% CIs for between-group GMC [GMT] ratios will be computed based on the antilog (base 10) of the corresponding CI limits for the difference in mean log10 concentrations [titers]. Differences between groups will be considered statistically significant if the 95% CI excludes 1.
4. Within-group (booster response) GMC [GMT] ratios will be computed based on the antilog (base 10) of the mean within-subject differences in log10 concentrations [titers], V6 minus V4, restricted to subjects who contribute evaluable immunogenicity data at each time point. Confidence intervals for within-group GMC [GMT] ratios will be computed as in (3), and booster responses will be considered statistically significant if the CI excludes 1.0.

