Similarly, while the functional immune response to multiple serotypes (types 6A, 7F, 9V, and 19A) was superior for the Prevenar 13 group as measured by OPA GMTS (and as illustrated in divergent reverse cumulative distribution [RCD] curves), the percentage of infants with a functional antibody response (OPA titer \geq 1:8) was substantial across all serotypes for both treatment groups – and was numerically higher for the PNEUMOSIL group for more serotypes (4 vs. 1) (Table 6). The small number of subjects with OPA data in all 3 cohorts limits what can be meaningfully concluded from these analyses.

IgG GMCs decreased substantially from 4 weeks post Vaccination 3 to just prior to the booster vaccination in both the PNEUMOSIL and Prevenar 13 groups. While GMCs were generally higher in the Prevenar 13 group at 4 weeks post Vaccination 3, pre-booster vaccination GMCs were generally comparable between groups due to the more substantial reduction in IgG concentrations in the Prevenar 13 group for serotypes that were significantly higher in the Prevenar 13 group post primary series. Both PNEUMOSIL and Prevenar 13 demonstrated a substantial booster effect across serotypes, indicating that the initial 3-dose series of both vaccines effectively ‘primed’ infants for boosting of immune responses.

Table 6. Percentage of OPA Seroresponders in the VAC-017 Infant Cohort – Primary Series (VAC-017)

Seroresponders on OPA Titers	PNEUMOSIL (N = 20)		Prevenar 13 (N = 20)		PNEUMOSIL vs Prevenar 13
	n (%) ^a	90% CI ^b	n (%) ^a	90% CI ^b	Difference (90% CI) ^c
OPA - Pn 1	15 (93.8)	73.60 - 99.68	11 (84.6)	58.99 - 97.19	9.1 (-15.55 - 36.11)
OPA - Pn 5	19 (95.0)	78.39 - 99.74	19 (95.0)	78.39 - 99.74	0.0 (-18.56 - 18.56)
OPA - Pn 6A	20 (100)	86.09 - 100.00	19 (100)	85.41 - 100.00	
OPA - 6B	19 (100)	85.41 - 100.00	19 (95.0)	78.39 - 99.74	5.0 (-12.35 - 22.97)
OPA - 7F	20 (100)	86.09 - 100.00	20 (100)	86.09 - 100.00	
OPA - 9V	20 (100)	86.09 - 100.00	20 (100)	86.09 - 100.00	
OPA - 14	19 (100)	85.41 - 100.00	18 (94.7)	77.36 - 99.73	5.3 (-12.15 - 24.01)
OPA - 19A	16 (94.1)	74.99 - 99.70	20 (100)	86.09 - 100.00	-5.9 (-26.41 - 11.01)
OPA - 19F	20 (100)	86.09 - 100.00	19 (95.0)	78.39 - 99.74	5.0 (-11.64 - 22.97)
OPA - 23F	20 (100)	86.09 - 100.00	20 (100)	86.09 - 100.00	

Abbreviations: CI = confidence interval, OPA = opsonophagocytic assay.

^a Number of responders (OPA titers \geq 1:8).

^b Exact CIs based on Clopper-Pearson method.

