Serotype	n	PNEUMOSIL (N=247)		Synflorix (N=250)		Treatment group comparison: PNEUMOSIL/Synflorix		
		GMT	(95% CI)	GMT	(95% CI)	GMT Ratio	(95% CI)	
Type 1	247	85.17	(71.34 – 101.69)	249	27.55	(22.96 – 33.06)	3.09	(2.40 – 3.98)*
Type 5	247	161.34	(139.94 – 186.02)	249	115.93	(98.85 – 135.97)	1.39	(1.12 – 1.72)*
Type 6A	247	1317.16	(1109.36 – 1563.88)	241	7.06	(5.83 – 8.56)	186	(144 – 241)*
Type 6B	243	913.52	(745.97 – 1118.70)	245	467.65	(365.27 – 598.73)	1.95	(1.42 – 2.69)*
Type 7F	247	1833.71	(1612.31 – 2085.51)	250	1586.75	(1392.62 – 1807.94)	1.16	(0.96 – 1.39)
Type 9V	242	141.72	(113.36 – 177.16)	249	376.77	(324.01 – 438.13)	0.38	(0.29 – 0.49)*
Type 14	244	1019.34	(816.53 – 1272.52)	247	1102.64	(878.56 – 1383.87)	0.92	(0.67 – 1.27)
Type 19A	247	148.59	(121.35 – 181.95)	236	11.09	(9.19 – 13.39)	13.4	(10.2 – 17.7)*
Type 19F	247	594.27	(509.98 – 692.49)	250	895.39	(784.96 – 1021.35)	0.66	(0.54 – 0.81)*
Type 23F	246	767.24	(648.95 – 907.10)	243	253.09	(197.10 – 325.00)	3.03	(2.25 – 4.09)*

Abbreviations: CI=confidence interval; GMT=geometric mean titer; OPA=opsonophagocytic activity

* Identifies statistically significant differences

Source: VAC-056 Final Statistical Report Table 14.2.2-2.2

Finally, a booster response was demonstrated for all 10 serotypes in both vaccine groups (data not shown). Post-booster IgG GMCs were significantly higher in the PNEUMOSIL group for 8 serotypes (1, 5, 6A, 6B, 7F, 14, 19A, 23F), and significantly higher in the Synflorix group for 2 serotypes (9V, 19F) (Table 10).

Table 10. Booster Response: Treatment Group IgG GMCs and Treatment-Group GMC Ratios (VAC-056)

Serotype	n	PNEUMOSIL (N=425)		Synflorix (N=209)		Treatment group comparison: PNEUMOSIL/Synflorix		
		GMC	(95% CI)	n	GMC	(95% CI)	GMC Ratio	(95% CI)
Type 1	425	5.73	(5.27 – 6.22)	209	2.45	(2.16 – 2.78)	2.34	(2.02 – 2.71)
Type 5	425	1.31	(1.21 – 1.41)	208	0.83	(0.75 – 0.92)	1.57	(1.38 – 1.79)
Type 6A	424	4.87	(4.41 – 5.39)	209	0.42	(0.35 – 0.49)	11.6	(9.67 – 14.0)
Type 6B	423	8.33	(7.71 – 9.00)	209	4.42	(3.98 – 4.90)	1.89	(1.65 – 2.15)
Type 7F	425	6.37	(5.88 – 6.90)	209	4.06	(3.65 – 4.50)	1.57	(1.37 – 1.80)
Type 9V	424	1.81	(1.67 – 1.95)	209	2.07	(1.87 – 2.30)	0.87	(0.76 – 0.99)
Type 14	420	6.85	(6.09 – 7.70)	204	4.62	(3.88 – 5.50)	1.48	(1.21 – 1.82)
Type 19A	423	3.97	(3.64 – 4.34)	205	0.94	(0.78 – 1.14)	4.22	(3.52 – 5.06)
Type 19F	416	6.16	(5.68 – 6.68)	204	9.70	(8.68 – 10.83)	0.63	(0.55 – 0.73)
Type 23F	425	4.08	(3.72 – 4.47)	209	2.13	(1.88 – 2.42)	1.91	(1.63 – 2.24)

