1.10. Study Rationale

Based on supportive data from a number of immunogenicity, carriage and clinical effectiveness studies, the WHO issued a position paper in 2012 recommending that countries adopt either a 3+0 or alternatively a 2+1 schedule for routine PCV administration to infants, with the primary doses of each schedule administered by 6 months of age and the booster dose of the 2+1 schedule administered at 9 months of age or later.²⁸ An updated WHO position paper issued in 2019 specifies that the booster dose of a 2+1 schedule should be administered at 9-18 months of age.²⁹ Which of the two PCV schedules a country adopts should be based on factors such as the epidemiology of pneumococcal disease in the country and coverage rates for EPI vaccines at 9 months of age or later. Because of the longer duration of protection that a booster dose may provide – particularly against serotypes of concern such as types 1 and 5 –, an increasing number of countries have adopted a 2+1 schedule in their EPI programmes, including India in 2018.

Given the TPP requirement regarding dosage schedule, and studies indicating higher seropositivity using an 8-week versus 4-week interval between primary doses,³⁰ study vaccine will be administered to infants enrolled in this Phase 3 trial at 6 weeks, 14 weeks, and 9-18 months of age. EPI vaccines will be co-administered with study vaccine during the primary dose visits, as well as during a study visit at 10 weeks of age (without co-administered study vaccine). This is an earlier schedule than the standard Gambian EPI schedule, as indicated in Table 12. Administering the infant EPI vaccines at this earlier schedule as part of the clinical trial ensures that all subjects are fully vaccinated, and avoids complications of missed vaccinations, and over-vaccination in the case of PCV.

Table 12. Gambian EPI Schedule for Children 0 to 18 Months Old*

Age at Immunization	Antigen
At birth	BCG, OPV, HepB
2 months	OPV, DTwP-HepB-Hib, PCV, RV
3 months	OPV, DTwP-HepB-Hib, PCV, RV
4 months	OPV, DTwP-HepB-Hib, PCV, IPV
9 months	OPV, measles-rubella, yellow fever
18 months	OPV, measles-rubella, DTwP, Vitamin A

Abbreviation: BCG, Bacillus Calmette–Guérin; OPV, Oral Polio Vaccine; RV, Rotavirus

*Should any changes to the EPI schedule in The Gambia occur before or during the study, the vaccines given alongside the

study vaccines will be modified accordingly to reflect the current programme.

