2.2. Study Endpoints

2.2.1. Primary Endpoints:

Immunogenicity:

1. Serotype-specific serum IgG GMCs measured 4 weeks post booster dose

Safety and Tolerability:

1. Number and severity of solicited local and systemic adverse events (AEs) through Day 6 post each vaccination
2. Number, severity and relatedness of all unsolicited AEs until 9 months of age, and from booster vaccination through a 4-week follow-up period
3. Number, severity, and relatedness of all serious adverse events (SAEs) through the entire study period

2.2.2. Secondary Endpoints:

Immunogenicity:

For Secondary Objective 1 (post-booster OPA GMTs):

- Serotype-specific serum OPA GMTs measured 4 weeks post booster dose

For Secondary Objective 2 (post-booster seroresponse rates):

- Percentage of subjects with serotype-specific serum IgG concentrations $\geq 0.35 \mu\text{g/mL}$ measured 4 weeks post booster dose
- Percentage of subjects with serotype-specific serum IgG concentrations $\geq 1.0 \mu\text{g/mL}$ measured 4 weeks post booster dose
- Percentage of subjects with serotype-specific serum OPA titers ≥ 8 measured 4 weeks post booster dose

For Secondary Objective 3 (post-primary IgG responses):

- Percentage of subjects with serotype-specific serum IgG concentrations $\geq 0.35 \mu\text{g/mL}$ measured 4 weeks post completion of primary vaccination
- Serotype-specific serum IgG GMCs measured 4 weeks post completion of primary vaccination

For Secondary Objective 4 (post-primary OPA responses):

- Percentage of subjects with serotype-specific serum OPA titers ≥ 8 measured 4 weeks post completion of primary vaccination
- Serotype-specific serum OPA GMTs measured 4 weeks post completion of primary vaccination

For Secondary Objective 5 (persistence of post-primary IgG responses):

- Percentage of subjects with serotype-specific serum IgG concentrations $\geq 0.35 \mu\text{g/mL}$ measured prior to booster dose
- Serotype-specific serum IgG GMCs measured prior to booster dose

For Secondary Objective 6 (persistence of post-primary OPA responses):

- Percentage of subjects with serotype-specific serum OPA titers ≥ 8 measured prior to booster dose
- Serotype-specific serum OPA GMTs measured prior to booster dose

For Secondary Objective 7 (booster effects):

- Ratio of serotype-specific serum IgG GMCs measured 4 weeks post booster dose to serotype specific IgG GMCs measured 4 weeks post completion of primary vaccination

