5.3.7. Secondary Objective 7: booster responses

Secondary objective 7 is to evaluate booster responses (serum antibody response GMCs and functional response GMTs) to PNEUMOSIL, alone and in comparison to booster responses to Prevenar 13 and Synflorix, from 4 weeks after completion of primary vaccination to 4 weeks after a booster dose (restricted to a subset of 50 subjects per group for functional responses). For each serotype and treatment group, the ratio of within-group GMCs and GMTs (V6 versus V4) will be reported, together with 95% CIs for these booster responses. The totality of the data (responses at V4, V6 and booster responses) will be descriptively compared between groups for clinical relevance.

In addition to tabulations of primary and secondary endpoints, immune response data will be summarized graphically at each of V4, V5, and V6, and over time using bar charts (OPA only) and reverse cumulative distribution (RCD) curves.

Due to the impact of the COVID-19 pandemic on clinic visit schedules, not all subjects selected for the OPA analysis at V4 contributed data at V5 and V6. Per Section 3.5, subjects not contributing V5 and V6 data were replaced with new subjects from the same field site and treatment group. To assess the robustness of Secondary Objective 7 results, the analysis of this objective will be repeated when restricting the sample to subjects who contributed both V4 and V6 data. The results of this sensitivity analysis and any related exploratory analyses will be only used to guide interpretation of the primary analysis results.

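### The rule for a significant booster response has no direction, so a fall below the post-primary level would earn the label, and no planned booster ratio uses the pre-booster sample

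*SAP*

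**What the plan says.** Secondary Objective 7 concerns the booster response from 4 weeks after the primary series (V4) to 4 weeks after the booster (V6). The endpoint in SAP 2.2 is the "Ratio of serotype-specific serum IgG GMCs measured 4 weeks post booster dose to serotype specific IgG GMCs" at V4, with the same ratio for OPA GMTs; the protocol's endpoint list agrees. SAP 5.1 item 4 computes it from "mean within-subject differences in log10 concentrations [titers], V6 minus V4", in subjects with data at both visits, and then sets the rule: "booster responses will be considered statistically significant if the CI excludes 1.0".

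SAP 5.3.7 adds only that, for each serotype and arm, "the ratio of within-group GMCs and GMTs (V6 versus V4) will be reported" with 95% CIs, and that the arms will be compared descriptively on V4, V6 and booster responses taken together. SAP 3.11 fixes the level: "All descriptive CIs will be at the 95% level, and all p-values assessed for statistical significance at the two-sided 0.05 level". None of these sections states a direction.

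The sample taken just before the booster (V5) is used in Objectives 5 and 6 (SAP 5.3.5 and 5.3.6), which report V5 levels and response rates by arm, and in the graphs in 5.3.7. It enters no booster ratio.

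**The concern.** A rule that only asks whether the interval excludes 1.0 suits a comparison between arms, where either direction is a finding. A booster response has a direction. Followed literally, item 4 gives the same label to a post-booster level significantly above the primary peak and to one significantly below it.

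The second issue is what the ratio measures. V6/V4 is the product of the change from V4 to V5 (mainly waning) and the change from V5 to V6 (the rise after the booster). Protocol 1.8.2 reports substantial waning before the booster in VAC-017, and more in one arm than the other: "pre-booster vaccination GMCs were generally comparable between groups due to the more substantial reduction in IgG concentrations in the Prevenar 13 group", for the serotypes that had been higher in that group after priming. A ratio against V4 therefore reflects how high the primary peak was as well as how well the booster worked.

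At stake is the wording of the booster conclusions by serotype. Protocol 1.10 justifies the booster by longer protection, "particularly against serotypes of concern such as types 1 and 5", and type 5 is the serotype whose earlier IgG data fall in the problem range.

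**Working it through.** **1. The plan's own precision figure.** SAP 3.2.1 assumes a CV of at most 1.5 and 220 infants per arm with 10% not evaluable, so n = 220 × 0.9 = 198.
- SD of ln(IgG) = √ln(1 + 1.5²) = 1.086.
- 95% CI for a ratio of 1.0 = exp(±t × 1.086 × √(2/198)) = 0.807 to 1.239. The SAP states 0.81 to 1.24, so it reproduces.

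SAP 3.2.3 says within-group booster ratios will be at least this precise. With zero within-subject correlation the paired formula gives the same standard error. On the plan's own benchmark, any observed V6/V4 below about 1/1.24 = 0.81 has a CI wholly below 1.0. At a correlation of 0.7 the cut-off is about 0.89.

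**2. Can such a ratio occur?** From protocol Table 8 (post-primary) and Table 10 (post-booster), VAC-056, type 5 IgG:
- PNEUMOSIL: 1.31/1.65 = 0.794.
- Synflorix: 0.83/1.20 = 0.692.

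The other nine PNEUMOSIL serotypes gave ratios from 1.32 (type 14) to 6.88 (type 6B).

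**3. The interval here if type 5 repeated.** Log-SDs from the printed CIs are ln(upper/lower)/3.92 × √n:
- PNEUMOSIL: ln(1.71/1.59)/3.92 × √1458 = 0.71; ln(1.41/1.21)/3.92 × √425 = 0.80.
- Synflorix: ln(1.26/1.14)/3.92 × √724 = 0.69; ln(0.92/0.75)/3.92 × √208 = 0.75.

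Paired CI = ratio × exp(±t × SD_d/√198), with SD_d² = s4² + s6² − 2ρ·s4·s6. The SAP calls ρ positive but gives no value, so it is varied here.

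| ρ (assumed) | PNEUMOSIL 0.79, VAC-056 SDs | PNEUMOSIL 0.79, CV 1.5 | Synflorix 0.69, VAC-056 SDs |
|---|---|---|---|
| 0 | 0.68-0.92 | 0.64-0.985 | 0.60-0.80 |
| 0.3 | 0.70-0.90 | 0.66-0.95 | 0.61-0.78 |
| 0.5 | 0.71-0.88 | 0.68-0.92 | 0.63-0.77 |
| 0.7 | 0.73-0.86 | 0.71-0.89 | 0.64-0.75 |

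Every interval lies below 1.0. If 0.79 were the true PNEUMOSIL ratio, the chance that the whole interval falls below 1.0 is 56% (ρ = 0) to 97% (ρ = 0.7) at CV 1.5, and 85% to over 99% with the VAC-056 SDs. If the true ratio were 1, the rule gives the label 5% of the time, half of it for a fall.

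**4. How much waning V6/V4 takes in.** V4 falls at 18 to 22 weeks of age (14 (+2) weeks, then 4 (+2) weeks), about 4 to 5 months. V5 falls at 9 to 19 months. The gap is therefore about 9 − 5 = 4 to 19 − 4 = 15 months.

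**5. Dependence on the peak.** Suppose two arms both have V5 = 0.5 and V6 = 4, but V4 is 2 in one and 1 in the other. V6/V4 is 2 against 4; V6/V5 is 8 in both. In the VAC-056 OPA data (Tables 9 and 11), the arm with the higher post-primary GMT has the lower ratio in 8 of 10 serotypes. For type 1, PNEUMOSIL has 344.53/85.17 = 4.05 and Synflorix 187.16/27.55 = 6.79, although PNEUMOSIL ends higher. In the IgG data this happens in none of the 8 common serotypes.

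**The case against.** V6/V4 is not a slip. It is the objective as worded and the prespecified endpoint in both documents. V6/V5 answers a different question and has its own denominator problem: an arm with better persistence would show a smaller rise. The protocol itself is cautious about fold rises in the VAC-017 toddlers, partly because of unequal baselines. This stands, and it is why V6/V4 should stay and V6/V5 should only support it.

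A reader might infer that V5 is ignored. It is not: Objectives 5 and 6 report it by arm with between-arm comparisons, and it is graphed. What cannot be formed from the planned tables is a paired V6/V5 estimate with an interval, because the SAP puts Objectives 5 and 6 in the Secondary per-protocol population and Objective 7 in the Primary one. The exploratory models in SAP 5.3.8 do examine V4-to-V5 time, but for booster change they use the V4-based ratio, which leaves waning and recall combined.

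A reader might also infer that the plan ranks the arms by how low their primary peak was. No between-arm CI, test or ranking of V6/V4 is planned; the comparison is descriptive and shows V4 and V6 beside the ratio. The peak effect appears in the earlier OPA data but not in the earlier IgG data.

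Finally, type 5 is the only PNEUMOSIL serotype whose IgG fell, and its OPA GMT rose: 409.87/161.34 = 2.5-fold, and 360.59/115.93 = 3.1-fold with Synflorix. The VAC-056 summary, "a booster response was demonstrated for all 10 serotypes in both vaccine groups (data not shown"), gives no definition, so it does not show that a decline was counted as a boost.

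**Conclusion.** The concern holds in a limited form. As written, the rule would label a post-booster level significantly below the post-primary level a significant booster response. The sponsor's type 5 IgG data make that a realistic case: at ratios of 0.79 and 0.69, the interval excludes 1.0 across every correlation and SD tried.

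This rests on carrying VAC-056 figures over. Priming there was three doses. The post-primary and post-booster samples are not the same set of subjects (1,458 and 425 for PNEUMOSIL; 724 and 208 for Synflorix). The correlation is assumed. After two priming doses V4 may differ; the PNEUMOSIL ratio would reach 1 if V4 were about 21% lower relative to V6 (1 − 0.79).

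Separately, no booster ratio isolates the rise after the booster, although the sample needed for it is collected. The documents do not support going further and saying that V6/V4 is the wrong endpoint or that the comparison between arms is invalid.

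The consequence is modest. The objective is secondary, the study is descriptive, no stated decision turns on the label, and a printed result such as 0.79 (0.70-0.90) shows a fall to anyone who reads it.

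**What to change.** 1. Keep V6/V4 as the prespecified Objective 7 endpoint.
2. In SAP 5.1 item 4 and 5.3.7, state that a significant booster response requires the lower 95% limit to exceed 1.0, and that an upper limit below 1.0 is reported as a post-booster level below the post-primary level. Under this rule, results like type 5 IgG at 0.79 or 0.69 would not be called booster responses, and the chance of the label when nothing has changed falls from 5% to 2.5%.
3. Add the paired within-subject V6/V5 ratio with 95% CI by arm (IgG in all subjects, OPA in the subset) as a supportive measure of the rise after the booster. Read it beside the V5 levels, because it also depends on its denominator.

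The cost is a clause of SAP wording and one extra table; V5 IgG and OPA are already measured. The downside is two ratios to explain, and some V6/V4 results lose the label.
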